3.2 Study Outcome Measures

3.2.1 Primary Outcome Measures

The **Primary Safety Endpoints** to be used to evaluate reactogenicity, safety and tolerability are as follows:

- The occurrence of solicited local site and systemic reactogenicity events from vaccination through 7 days after each dose of vaccine is administered
- The occurrence of study withdrawals throughout the study
- The occurrence of discontinuation of study vaccination during the study

- The occurrence of unsolicited vaccine-related adverse events (AE), including laboratory AE, from first vaccination through 28 days after the last dose of vaccine is administered

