- Confirm ongoing consent prior to performing any study procedures. Review any SAEs that have occurred since the last visit as well as update the medical history and concomitant medications as necessary, to support an SAE.
- Record oral temperature, pulse, and blood pressure
- Collect approximately 15 mL of venous blood:
 - 15 mL for cryopreservation of PBMC, for memory B cell (5 mL) and effector T cell assays (10mL)
 - Collect plasma from PBMC tubes

7.5 **Early Termination Visit**

Upon voluntary withdrawal of participation or any other reason for early termination from the study attempt to complete a clinic visit to include:

- Obtain an interim medical history and concomitant medication information and record on the appropriate case report form.
- Assess reactogenicity and review memory aid if early termination visit occurs within 7 days of any vaccination.
- Assess for unsolicited AEs if visit occurs within 28 days of third vaccination

- Assess for SAE during all early termination visits. Participants will be asked to be followed until resolution of any AEs.
- Record oral temperature, pulse, and blood pressure
- Perform a targeted physical examination, if indicated based on review of medical history
- Obtain serum samples for laboratory safety assays if visit occurs ≤ 28 days after third vaccination

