7.6 Unscheduled Visit

If an unscheduled visit occurs, a member of the clinical study team (PI, Co-Investigator, Study Coordinator, or Clinical Nurse) will interview and evaluate the participant to determine the cause of the visit and provide care as needed, and information will be documented on a supplemental visit eCRF.

Any of the following activities may be performed during this visit:

- Review of reactogenicity (if within 7 days of last vaccination), unsolicited non-serious AE information (if within 28 days of last vaccination), or any SAE information (anytime within study)
- Review of concomitant medications (if within 28 days of last vaccination)
- Obtain interim medical history
- Targeted physical examination, if indicated
- If the unscheduled visit is for eligible diarrhea ([section 8.2.2](#)), then a stool specimen will be collected for culture.
- If the unscheduled visit is grade 3 local injection site reactogenicity event in a participant in the ID cohort and the event is within 7 days of a dose administration (as described at the end of [section 8.1](#)), then measurements of the reaction and a digital photo will be performed. Unscheduled daily visits by the study team will continue until the injection site reaction is deemed stable or returns to a grade 2 or lower severity.
- Upon the judgement of the clinical investigator, clinical laboratory assessments may be performed to evaluate an AE and medications (e.g., analgesics) may be recommended to treat an AE

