8.2 Laboratory Evaluations

8.2.1 Clinical Laboratory Evaluations

A total of 2 mL blood will be collected for screening clinical labs for the evaluation of eligibility. If screening laboratory results are out of range value, they may be repeated once provided there is an alternative explanation for the out of range value. Participants must have acceptable screening laboratory findings within 7 days prior to enrollment. The acceptable ranges for study eligibility are listed in [Appendix B](#).

For the assessment of safety, a total of 2 mL of blood will be collected for clinical safety labs on visit 7, about 4 weeks after the third dose of vaccine. These include a CBC with differential for WBC, Hg, ANC, Platelet count, creatinine, albumin, and ALT. In addition, 2 mL of blood will be collected at visit 6 (7-days post-third dose of vaccine) for ALT, serum bilirubin, and creatinine. The grading of toxicity for clinical safety lab values that are not in the normal range is

provided in [Appendix C](#).

All women will have a urine pregnancy test performed during screening and a urine pregnancy test on the vaccination days. The results of the urine pregnancy test must be negative prior to enrollment in the study, and prior to each vaccination.

For those laboratory tests run as part of a panel of tests, but not required by the protocol, the site is required to do the following:

- Enter all non-required lab results into the database in the comments section of the eCRF.
- When a result is abnormal per the site normal laboratory reference range, the result must be:
 - Entered in the comments section of the database including assessment for clinical significance by site PI,
 - An AE generated and followed until resolution if clinically significant based on assessment by the site PI,
 - If clinically significant, graded according to either the toxicity tables in [Appendix C](#) or if a grading scale is not available, the PI should use the guidance for AE grading.

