⁶Review to include assessments of: 1) injection site necrosis within 7 days of vaccination, 2) urticaria, laryngospasm, bronchospasm, or anaphylaxis determined to be related to vaccine and within 7 days of vaccination, 3) facial nerve neuropathy, confirmed by an investigator and determined to be related to vaccine.

⁷Assess reactogenicity and review memory aid if early termination occurs within 7 days of any vaccination

⁸ AE assessment to include (as applicable): 1) Assess reactogenicity (if within 7 days of last vaccination), unsolicited non-serious AE information (if within 28 days of last vaccination), or any SAE information (anytime within study) 2) Upon judgement of the clinical investigator, clinical laboratory assessments may be performed to evaluate an AE and medications (e.g analgesics) may be recommended to treat an AE.

⁹Visits 1-7: Provide instructions to women participants to avoid pregnancy through the 28 days from receipt of the last dose of vaccine.

¹⁰Early Termination Visit is to include: assess reactogenicity and review memory aid if early termination occurs within 7 days of any vaccination; assess for SAE during all early termination visits; obtain serum samples for laboratory safety assays if visit occurs <28 days after third vaccination.

Intradermal cohorts												Unscheduled visit, upon investigator judgement	Early Termination ¹¹
Study Visit (V)	screen	1	2	3	4	5	6	7	8	9			
Study Day	-7 to -4	1	8	22	29	43	50	71	128	223			
Window			±1d	±2d	±1d	±2d	±1d	±3d	±1w	±2w			
Study Week		0	1	3	4	6	7	10	18	32			
Informed Consent	X												
Confirm Ongoing Consent		X	X	X	X	X	X	X	X	X			
Eligibility Review	X	X	X	X	X	X	X	X	X				
Collection of demographics	X												
Medical History	X	X	X	X	X	X	X	X	X	X	[X]		
Concomitant Medications	X	X	X	X	X	X	X	X	X	X	[X]		
Physical Exam	X	X ²	X ²	X ²	X ²	X ²	X ²	X ²	X ²		X	[X]	
Vitals Signs	X ³	X ³	X ³	X ³	X ³	X ³	X ³	X ³	X ³	X ³	X	[X]	
Urine pregnancy test ^{4,10}	X	X		X		X							
VACCINATION		#1		#2		#3							
Pre-vaccination & Post-vaccination assessment		X ⁶		X ⁶		X ⁶							
Memory Aid and thermometer (d)distribute, (c) collect Memory Aid		d	c	d	c	d	c				[c] ⁸		
Confirm date & time of next Visit		X	X	X	X	X	X	X	X				
Adverse Event (AE) / Serious AE review		X	X ^{5,7}	X	X ^{5,7}	X	X ^{5,7}	X ⁷	X ¹	X ¹	X ^{5,9}	X	
Screening stool	X												
Saliva/Oral Fluid for Ab		X	X	X	X	X	X	X			Also may occur: Stool culture, as when indicated in section 8.2.2;		
Stool for ELISA Ab		X	X	X	X	X	X	X					

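### Early-termination safety labs are keyed to the third vaccination, so a participant who leaves after dose 1 or 2 has no required post-vaccination laboratory test

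*Protocol*

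**What the plan says.** Protocol Section 7.5 lists what to do at an early-termination visit. Two items depend on the third dose: "Assess for unsolicited AEs if visit occurs within 28 days of third vaccination" and "Obtain serum samples for laboratory safety assays if visit occurs ≤ 28 days after third vaccination". Other items in the same list do not. Reactogenicity is assessed within 7 days of any vaccination, and serious events carry no condition: "Assess for SAE during all early termination visits. Participants will be asked to be followed until resolution of any AEs".

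Appendix A footnotes 10 (oral and sublingual) and 11 (intradermal) restate the laboratory rule as "obtain serum samples for laboratory safety assays if visit occurs <28 days after third vaccination". They name reactogenicity, serious events and labs, but not unsolicited adverse events. The grid above them has an unqualified mark for AE/SAE review in the early-termination column, whereas Visits 8 and 9 carry the SAE-only footnote.

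Elsewhere the anchor is the last dose. The primary endpoint in Section 3.2.1 covers unsolicited vaccine-related events, "including laboratory AE, from first vaccination through 28 days after the last dose of vaccine is administered". Section 4 collects unsolicited events to 28 days after the last vaccination. Section 7.6 reviews, at unscheduled visits, "unsolicited non-serious AE information (if within 28 days of last vaccination").

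On scheduled labs, Section 8.2.1 places a blood count and chemistry panel at Visit 7, about four weeks after dose 3, and adds: "In addition, 2 mL of blood will be collected at visit 6 (7-days post-third dose of vaccine) for ALT, serum bilirubin, and creatinine". At an unscheduled visit, labs are at the investigator's judgement and serve to evaluate an adverse event.

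**The concern.** The endpoint and the early-termination rule run on different clocks. Someone who leaves after dose 1 or 2 never has a third vaccination, so a condition counted from that date cannot be met, and neither conditional item in Section 7.5 is triggered.

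The laboratory item matters most because nothing else in the schedule replaces it. The Safety Analysis population (Protocol 11.4.1) takes in every eligible participant given at least one dose, and SAP Section 9.3 sets the adverse-event denominator at the total population size. An untested leaver therefore counts in the denominator of a primary safety summary but has no required test that could put them in the numerator for a laboratory event. The Grade 3 laboratory criterion in Section 9.5 also cannot count a result that was never drawn. With 12 vaccinees per cohort, one or two such participants are a visible share.

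**Working it through.** **1. The plan's own precision figures.** With no events among n, the exact two-sided 95% upper limit is 1 − 0.025^(1/n). For n = 10 this is 0.3085 (30.8% as stated), for n = 20 it is 0.1684 (16.8%), and for n = 60 it is 0.0596 (6.0%). All three figures in Protocol 11.2 reproduce, and this point does not dispute them.

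**2. When the first scheduled safety lab falls.** Nominal study days are from Appendix A.

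| Route | Dose 1 | Dose 3 | Visit 6 | Visit 7 | Dose 1 to dose 3 | Dose 1 to Visit 6 | Dose 1 to Visit 7 |
|---|---|---|---|---|---|---|---|
| Oral, sublingual | 1 | 29 | 36 | 57 | 28 days | 35 days | 56 days |
| Intradermal | 1 | 43 | 50 | 71 | 42 days | 49 days | 70 days |

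There are no scheduled safety labs between dose 1 and dose 3. SAP Section 15 adds that the Visit 6 labs were not obtained in Cohorts A to C, so in those cohorts the first scheduled test was Visit 7, 56 days after dose 1.

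**3. The endpoint window for a leaver.** The window closes 28 days after the last dose.
- After dose 1 only: Day 1 + 28 = Day 29, on every route.
- After dose 2: Day 15 + 28 = Day 43 (oral, sublingual), or Day 22 + 28 = Day 50 (intradermal).

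Visits 6 and 7 are defined from dose 3, and the early-termination draw is conditional on dose 3. For someone who has left, no rule requires a lab inside these windows.

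**4. Unsolicited adverse events.** Events since the last visit are reviewed at Visit 2 (Day 8) and Visit 4 (Day 22 oral and sublingual, Day 29 intradermal). Unsolicited events are also covered by the post-vaccination assessment at Visit 3 (Day 15 or Day 22). What can be missed is an event after the last attended visit, and only if the site follows Section 7.5 or the footnotes rather than the grid.

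**5. What untested leavers do to precision.** The documents give no expected number of early leavers, so 0, 1 and 2 of 12 vaccinees in a cohort are assumptions. The zero-event upper limit for laboratory events over those actually tested is:
- 12 tested: 1 − 0.025^(1/12) = 26.5%
- 11 tested: 1 − 0.025^(1/11) = 28.5%
- 10 tested: 1 − 0.025^(1/10) = 30.8%, with 2/12 = 16.7% untested

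**The case against.** The best defence is that the drafters treat the third and the last dose as the same thing. Section 9.1 does so when it defines the unsolicited-event period as running from first vaccination to 28 days after the last dose, with the word third in brackets. On that reading Section 7.5 states only when the window ends, and a visit before dose 3 is already inside it. This may have been the intent, but Section 7.5 does not say it. Its own list uses any vaccination for reactogenicity and every early-termination visit for serious events, so a site would reasonably take the third-dose wording at face value.

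A reader might infer that an early leaver gets no unsolicited-event check at all. The documents do not support that: the grid marks the review, Visits 2 to 4 include one, Section 7.5 requires an interim medical history, and Section 5.3.4 asks for an early-withdrawal assessment, by telephone if necessary. What remains is a conflict between passages.

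A reader might also infer that everyone stopped for a reaction is affected. Section 5.3.4 separates stopping vaccination from leaving the study and asks that those who stop be monitored further, if they agree and it is safe. Only those who leave fall under the early-termination rule.

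Finally, untested participants are not silently shown as normal everywhere. The SAP laboratory severity tables have a Missing column, and SAP Section 6.1 bases categorical percentages on the non-missing sample. This objection stands for those tables. It does not reach the adverse-event incidence summaries, which use the total population.

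**Conclusion.** The laboratory point holds. As written, leaving after dose 1 or 2 means no required post-vaccination safety test, against a primary endpoint that includes laboratory events from the first dose. The unsolicited-event point holds only as an inconsistency, confined to the interval since the last attended visit. The conclusion assumes that sites apply Section 7.5 literally and that discretionary labs at unscheduled visits are not a substitute.

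The effect cannot be sized from the documents, because they give no early-termination rate. A reader might take the gap between 12 enrolled and 10 evaluable vaccinees and multiply it over the cohorts. That is not supported: evaluability also requires specimens through 7 days after dose 3, a non-evaluable participant has not necessarily left or missed dose 3, and the minimum can be restored by further enrolment.

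Cohort E may also look like proof, since no participant there received dose 3. SAP Section 15 attributes the missed dose and the missed Visits 6 to 9 to a national lockdown, so Section 7.5 did not cause the missing labs.

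**What to change.** In Section 7.5 and Appendix A footnotes 10 and 11, key both the unsolicited-event assessment and the safety labs to the last vaccination received. Add the unsolicited-event assessment to the two footnotes so that they agree with the grid mark. Use one limit: the text now includes day 28 and the footnotes exclude it. This brings the early-termination rule into line with Sections 3.2.1, 4 and 7.6, and it changes no dosing or stopping rule.

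The cost is a wording change in three places and one 2 mL safety sample, the volume Section 8.2.1 uses for its panels, for each early leaver who attends in person. Appendix A already lists 10 mL of blood outside the numbered visits. The gain is limited in the same way: Section 7.5 only asks sites to attempt a clinic visit, so leavers reached by telephone would still have no test.

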7.6 Unscheduled Visit

If an unscheduled visit occurs, a member of the clinical study team (PI, Co-Investigator, Study Coordinator, or Clinical Nurse) will interview and evaluate the participant to determine the cause of the visit and provide care as needed, and information will be documented on a supplemental visit eCRF.

Any of the following activities may be performed during this visit:

- Review of reactogenicity (if within 7 days of last vaccination), unsolicited non-serious AE information (if within 28 days of last vaccination), or any SAE information (anytime within study)
- Review of concomitant medications (if within 28 days of last vaccination)
- Obtain interim medical history
- Targeted physical examination, if indicated
- If the unscheduled visit is for eligible diarrhea ([section 8.2.2](#)), then a stool specimen will be collected for culture.
- If the unscheduled visit is grade 3 local injection site reactogenicity event in a participant in the ID cohort and the event is within 7 days of a dose administration (as described at the end of [section 8.1](#)), then measurements of the reaction and a digital photo will be performed. Unscheduled daily visits by the study team will continue until the injection site reaction is deemed stable or returns to a grade 2 or lower severity.
- Upon the judgement of the clinical investigator, clinical laboratory assessments may be performed to evaluate an AE and medications (e.g., analgesics) may be recommended to treat an AE

8 STUDY PROCEDURES/EVALUATIONS

8.1 Clinical Evaluations

Medical History: Will be obtained by interview of the participants. Participants will be queried regarding a history of significant medical disorders of the head, eyes, ears, nose, throat (HEENT), mouth, cardiovascular system, lungs, gastrointestinal tract, liver, pancreas, kidney, urologic, nervous system, blood, lymph glands, endocrine system, musculoskeletal system, skin, and genital/reproductive tract. A history of any allergies, cancer, immunodeficiency, psychiatric illness, substance abuse, and autoimmune disease will be solicited.

Medication History: All concomitant medications (e.g., vitamins, antacids, analgesics, prescription medications) taken 28 days prior to vaccination will be recorded in the concomitant medication data collection form. Any medications taken during the 7 days following a dose of vaccine are to be recorded on the participant's memory aid and/or reported to a research team member upon follow up clinic visit. All analgesics and prescription medications from 8 to 28 days post-vaccination will be recorded in the concomitant medication data collection form. Assessment of eligibility also will include a review of permitted and prohibited medications (per the exclusion criteria).

Physical Examination: At screening (Days -7 through -4) appropriate study personnel will record oral temperature, pulse and blood pressure and perform an abbreviated physical examination to assess general wellness which will include the following areas/systems: HEENT; lymph nodes; skin; pulmonary; cardiovascular; abdominal; neurological; and musculoskeletal systems. The physical examination should specifically address issues identified by the medical history of the participant. At following visits including enrollment, oral temperature, pulse, and blood pressure will be recorded and a targeted physical examination may be conducted if indicated based on review of medical history.

Reactogenicity Assessments: Will include brief history for assessment of AE/SAEs just prior to and following vaccination (Days 1, 15, and 29 for oral/SL; Days 1, 22, and 43 for ID), which includes an assessment of systemic and local reactions according to [section 9.1](#). Participants will be examined at the end of a 30 minute observation period following each vaccination for the SL and ID cohorts, and at the end of a 90 minute observation period for oral cohorts.

Memory Aids: All participants will complete a subject memory aid distributed after each vaccination. Subject memory aids will be reviewed with the participant for solicited AEs. Participants will be instructed to record daily oral temperature on the memory aid. Participants will be asked about the occurrence of unsolicited AE/SAEs during visits 2 (Day 8, oral/SL/ID), 4

(Day 22, oral/SL; Day 29, ID), and 6 (Day 36, oral/SL; Day 50, ID). Following review, the appropriate source document and electronic case report form (eCRF) will be completed by the study staff. For illiterate participants, either a literate member of the household will be trained to help to fill out the memory aid or a field staff member will be identified to visit the household to help with the completion of the memory aid. Memory aids will not be retained as a source document.

Adverse Event Review: It is not anticipated that AEs of diarrhea and/or vomiting (or other signs of enterotoxicity) will be common or severe in this study, based on the previous experience with oral and SL dmLT or ID dmLT clinical trials. However, an evaluation of any participant who experiences diarrhea will be performed by the study staff, if it occurs within 7 days of dosing. The determination of severity diarrhea is based as follows:

Clinical Sign	Normal	Mild (Grade 1)	Moderate (Grade 2)	Severe (Grade 3)
Diarrhea	Normal or 1-2 loose stool per 24 hours	3 loose stools per 24 hours	4-7 loose stools per 24 hours	8 or more loose/watery stools per 24 hours or require outpatient IV hydration, ED visit or hospitalization for diarrhea

The assessment of dehydration will be performed in clinic by a study investigator, according to [Table 2](#) below. The management of dehydration will be guided according to [Table 2](#) below, but is ultimately to be managed at the discretion of the investigator. The assessment of severity of diarrhea and level of dehydration and treatment will be documented in the appropriate source document. A description for the conditions leading to the performance of stool cultures is described in [section 8.2](#).

Table 2: Assessment of Dehydration and Treatment Guidance

Clinical Assessment	General Appearance	Well, Alert	Restless, Irritable	Lethargic or Unconscious
	Eyes	Normal	Sunken	Sunken
	Thirst	Normal	Thirsty, drinks eagerly	Unable to Drink
	Skin Turgor	Normal	Slow Return	Very Slow Return
Degree of Dehydration	No signs of dehydration		Some Dehydration	Severe Dehydration
Treatment Guidance	Reassure and educate on signs of dehydration	Provide ORS and reassess after ORS completed, until no dehydration	Provide ORS and consider IVF, reassess and repeat until no dehydration	

ORS = oral rehydration solution

IVF = intravenous fluid

For participants in the ID cohorts, should there be any grade 3 local injection site reactogenicity (i.e., within 7 days of dose administration); the research staff will request the participant be evaluated by the study team to mark the widest edges of the respective reaction (e.g., redness, induration, or bruising), measure, and record on the CRF. Furthermore, a digital photo of the site will be taken by the study team. Additional measurements and a photo should be taken on a daily basis by the study team until the injection site reaction is deemed stable or returns to a grade 2 or lower severity.

